3.3.3 Handling of Unscheduled Visits, Retest and Early Discontinuation Data

Any data collected at unscheduled visits, retest or early discontinuation assessments will be listed, and will be included in any definitions of maximum value, minimum value or last value within the relevant study period.

Measurements collected from unscheduled visits, retest or early discontinuation assessments may also be considered in the analysis visit window. In the case of a missing value at a scheduled visit, which is then followed by a non-missing value at an unscheduled or retest assessment within the same visit window, the non-missing value at the unscheduled/retest assessment will be used.

3.3.4 Multiplicity/Multiple Comparisons

No adjustment for multiplicity will be performed.

3.3.5 Handling of Protocol Deviations in Study Analysis

Important protocol deviations (IPDs) will be listed and tabulated in the Clinical Study Report (CSR). IPDs are defined as deviations that may greatly impact the completeness, accuracy, and/or reliability of the study data or that may significantly affect a subject's rights, safety, or well-being. They may include but not be limited to:

- Subjects who do not meet the inclusion criteria
- Subjects who meet any of the exclusion criteria
- Subjects who use one or more disallowed medication (for any reason, unless otherwise specified) during the treatment period
- Subjects who received the incorrect IP or study dose

IPD in this study will include, please refer to Protocol Deviations Management Plan (PDMP) table 2: list of potential protocol deviations. All important protocol deviations will be identified and documented prior to unblinding of the data.

In addition, COVID-19 related protocol deviations and issues will be captured for reporting.

3.3.6 Handling of missing data

No imputations will be made for any missing data. In the case where prior or concomitant medication start/end dates are partial, but are required in the calculation of administration time of the study medication, temporary imputed variable(s) will be set to the earliest/latest possible date for medication start/end dates respectively. Partial dates handling rules of AEs are described in Appendix 1. All available dates without imputation will be listed.

4 STATISTICAL ANALYSIS

This section provides information on definitions, derivation and analysis/data presentation per domain.

4.1 Study Population

The domain study population covers subject disposition, analysis sets, protocol deviations, demographics, baseline characteristics, medical history (including surgical history), prior and concomitant medication, and study drug exposure.

4.1.1 Subject Disposition and Completion Status

4.1.1.1 Definitions and Derivations

All subjects who were screened will be used for reporting of disposition. The number of subjects screened, screen failures with justifications will be summarized using all subjects enrolled; the number and percentage of subjects randomized, subjects who received treatment, subjects who completed the study, and subjects who discontinued from the study will also be summarized by treatment group.

4.1.1.2 Presentation

A summary table will be presented specifying respectively:

- Number of subjects screened
- Number of subject screened but not randomized
 - Reasons for screened but not randomized
 - Did not meet inclusion/exclusion criteria

- Lost to follow-up
- Withdrawal of consent
- Other (Include withdrawal due to limited number of subjects for randomized)
- Number of subjects randomized
- Number of subjects who received study treatment
- Number of subjects randomized but not received study treatment
- Number of subjects who completed the study
- Number of subjects who discontinued from the study
 - Reasons for discontinuation from the study
 - Death
 - Lost to follow-up
 - Withdrawal by Subject
 - Pregnancy
 - Adverse event
 - Sponsor decision
 - Other
 - Due to COVID-19 pandemic

4.1.2 Analysis Sets

Agreement and authorization of subjects included/excluded from each analysis set will be conducted prior to the database lock (DBL).

4.1.2.1 Definitions and Derivations

Analysis sets will be summarized by treatment group for participants randomized. The number of participants included or excluded (and reason) from an analysis set within each treatment group will be presented.

4.1.2.2 Presentation

Summary of analysis populations will be provided. Participants excluded from any analysis population will be listed.

4.1.3 Protocol Deviations

4.1.3.1 Definitions and Derivations

Protocol deviations will be reviewed on a case-by-case basis by the medical advisors and statisticians prior to unblinding. The Statistical Analysis Plan may be revised due to these reviews.

4.1.3.2 Presentation

The numbers and the percentages of subjects with each important protocol deviations will be presented for as-treated population. Only subject level protocol deviations will be listed for as-treated population. In addition, issues reported due to COVID-19 pandemic, regardless of whether the type of issue is considered a protocol deviation or not, will be listed.

4.1.4 Demographics

4.1.4.1 Definitions and Derivations

Demographic data will be summarized for as-treated population. No statistical testing will be carried out for demographic or other baseline characteristics.

Following demographic will be reported for this study:

- Age (years) - calculated relative to date of consent
 - $\text{Age (years)} = (\text{Date informed consent signed} - \text{Date of Birth}) / 365.25$.
- Sex:
 - Male
 - Female
- Ethnicity:
 - Not Hispanic or Latino
 - Hispanic or Latino
- Race
 - Asian
 - Other

4.1.4.2 Presentation

Continuous data will be summarized using number of observations (n), mean, SD, median, minimum, maximum for non-missing observations; categorical data will be summarized using frequency counts and percentages for non-missing observations.

Listings of subjects' demographic will be provided.

4.1.5 Baseline Characteristics

4.1.5.1 Definitions and Derivations

Baseline characteristics will be summarized for as-treated population.

Following baseline characteristics will be reported for this study:

- Height (cm)
- Weight (kg)
- Body Mass Index (kg/m²)
 - BMI (kg/m²) = weight (kg)/ (height (m))²

4.1.5.2 Presentation

Continuous data will be summarized using number of observations (n), mean, SD, median, minimum, maximum for non-missing observations.

Listings of subjects' baseline characteristics will be provided.

4.1.6 Medical and Surgical History

4.1.6.1 Definitions and Derivations

Medical History and Surgical History information are collected in “Medical history” and “Surgical History” CRF page and will be summarized and listed for as-treated population.

Medical history and Surgical history will be summarized by using the Medical Dictionary for Regulatory Activities (MedDRA) central coding dictionary, Version 23.1 or higher codes of System Organ Class (SOC) and Preferred Term (PT).

4.1.6.2 Presentation

Numbers and percentages of subjects will be presented by treatment group for each System Organ Class (SOC) and Preferred Term (PT). If a medical history or surgical history condition occurs more than once for a subjects per level of summarization the subjects is only counted once per MedDRA SOC or PT. SOC's are to be sorted by total decreasing frequency. PT's are to be sorted by total decreasing frequency within each SOC. If SOC's or PT's have the same total frequency they are to be sorted alphabetically.

4.1.7 Allergy History

4.1.7.1 Definitions and Derivations

Allergy History information are collected in “Allergy History” CRF page.

4.1.7.2 Presentation

Subjects will be listed for as-treated population.

4.1.8 Concomitant Medications

4.1.8.1 Definitions and Derivations

Prior and concomitant medication data will be captured from “Concomitant Medications” page on CRF. Medications will be coded using the World Health Organization (WHO) Drug Dictionary Global September 2020 B3 or higher. The number and percentage of subjects with prior and concomitant medications will be tabulated by Anatomic Therapeutic Chemical (ATC) level 4 and Drug Preferred Name by treatment arm. Any disallowed concomitant medications taken during study treatment will also be tabulated.

Prior medications are defined as medications which started and stopped prior to the administration of study treatment. Concomitant medications are defined as medications which are taken on or after the administration of study treatment (reference start date).

Subjects taking the same medication multiple times in a given study period will only be counted once for each term in the drug dictionary hierarchy being presented.

4.1.8.2 Presentation

The number and percentage of subjects experiencing each prior and concomitant medication will be presented by ATC/PT by treatment for the as-treated population. ATC terms are to be sorted by total decreasing frequency. PTs are to be sorted by total decreasing frequency within each ATC. If ATCs or PTs have the same total frequency they are to be sorted alphabetically.

4.1.9 Study Drug Exposure and Compliance

4.1.9.1 Definitions and Derivations

Extent of exposure to IP is defined as the number of days between the start and the end dates of study drug. As there is only a single dose for nirsevimab, extent of exposure will be presented as Yes/No.

Exposure

- The answer for the question "Treatment" as entered into the “Dose” eCRF page will be used to identify extent of exposure.

4.1.9.2 Presentation

The number (%) of subjects will be summarised across all subjects by treatment with the following variables for as-treated population.

- Number (%) of subjects who take complete dose.
- Number (%) of subjects who take incomplete dose.
- Overdose Occurrence
- Medication Error Occurrence

4.1.10 Procedures

4.1.10.1 Definitions and Derivations

Procedures data will be captured from “Procedures” page on CRF.

4.1.10.2 Presentation

Subjects will be listed for as-treated population.

4.2 Endpoint Analyses

This section covers details related to the endpoint analyses such as primary and secondary analyses.

Table 5. Objectives and Endpoints:

Statistical category	Endpoint	Population	Details in section
To evaluate serum concentrations of nirsevimab	Summary of nirsevimab serum concentrations	PK population	4.2.1
	Estimated PK parameters (C _{max} , T _{max} , AUC ₀₋₁₅₀ , and others if data permit)	PK population	4.2.1
To evaluate the safety and tolerability of nirsevimab when administered as a single fixed IM dose of 300 mg to healthy Chinese adult subjects	Occurrence of all TEAEs, TESAEs, AESIs, and NOCDs	As-treated Population	4.2.2
	Clinical laboratory assessments	As-treated Population	4.2.2
	Vital signs	As-treated Population	4.2.2
To evaluate ADA responses to nirsevimab in serum	Incidence of ADA to nirsevimab in serum	As-treated Population	4.2.2

4.2.1 Primary Endpoint

4.2.1.1 Definition

This section covers details related to pharmacokinetics endpoints and analyses.

Pharmacokinetic analysis of the serum concentration data for nirsevimab will be performed at IQVIA, Overland Park, Kansas, United States. Pharmacokinetic parameters will be derived using standard noncompartmental methods using Phoenix WinNonlin® 8.1 or higher (Pharsight Corp., Certara Company, Princeton, New Jersey, United States); and/or SAS® Version 9.4 or higher. Graphics will be prepared with SAS® Version 9.4, or higher. Actual elapsed sampling times, if available, will be used for the final PK parameter calculations.

The PK concentration, collection time and collection time deviation will be presented in one listing. Data from subjects excluded from the PK analysis set will be included in the data listings, but not in the summaries. Extra measurements (such as unscheduled or repeat assessments) will not be included in the summary tables, but will be included in subject listings.

Concentration-time data will be summarized by scheduled time.

Samples that are collected outside the analysis visit windows will be flagged for identification in the listing. They will not be included in the concentration summary.

Figures of arithmetic mean (\pm SD) serum concentrations versus nominal time will be prepared on linear and semi-logarithmic scales. Figures of individual serum concentrations versus actual time will be presented by subject on linear and semi-logarithmic scales.

Calculation or derivation of pharmacokinetic variables

The PK analysis will be performed using the PK population.

Where possible, the following serum PK parameters will be determined for nirsevimab using the serum concentration data.

C_{\max}	Observed maximum serum concentration ($\mu\text{g/mL}$), taken directly from the individual concentration-time curve
T_{\max}	Time to reach maximum serum concentration (day), taken directly from the individual concentration-time curve
AUC_{0-150}	Area under the serum concentration-curve from time zero to 150 days, calculated by linear up/log down trapezoidal summation

Additional calculations may be performed at the discretion of the PK scientist as appropriate.

4.2.1.2 Presentation

Pharmacokinetic parameters will be summarized using descriptive statistics as described in Section 3.3. A subject listing of individual PK parameters will also be provided.

4.2.1.3 Handling of BLQ and Missing Values

Individual concentrations which are BLQ will be reported as not quantifiable (NQ) with the lower limit of quantitation (LLOQ) defined in the listings, tables, and figures as appropriate. Any missing values reported as no sample (NS) will be excluded from the summary tables and corresponding figures.

For descriptive statistics:

- if, at a given time point, 50% or less of the plasma concentrations are NQ, the Gmean, CV, Geometric SD, $Gmean \pm gSD$, arithmetic mean and SD are calculated by substituting the LLOQ for values which are NQ
- if more than 50%, but not all, of the concentrations are NQ, the Gmean, CV, Geometric SD, $Gmean \pm gSD$, arithmetic mean, and SD are reported as not calculable (NC). The max value will be reported from the individual data, and the min and median will be set as NQ
- if all the concentrations are NQ, no descriptive statistics will be calculated for that time point. The Gmean, arithmetic mean, median, minimum, and maximum are reported as NQ and the CV, Geometric SD, $Gmean \pm gSD$, and SD as NC
- The number of values below LLOQ are reported for each time point along with the total number of collected values

Three observations \geq LLOQ are required as a minimum for a plasma concentration or PK parameter to be summarised. Two values are presented as a minimum and maximum with the other summary statistics as NC.

For graphical presentation, postdose BLQ values will be set to $\frac{1}{2}$ of LLOQ values for individual plots. For mean plots, BLQ values will be handled as described for concentration descriptive statistics.

For PK analysis, predose samples that are BLQ or missing will be assigned a numerical value of zero for the calculation of PK parameters. Any anomalous concentration values observed at predose will be identified in the study report and used for the computation of PK parameters. Pharmacokinetic parameters will be computed, listed, and included in all summaries if the anomalous value is not greater than 5% of C_{max} . If the anomalous value is greater than 5% of C_{max} , PK parameters will be calculated and listed, but affected profiles

will be excluded from summaries for both the observed concentrations and derived PK parameters. Handling of affected profiles will be documented in the PK analysis review form with a description of how the value was treated for the computation, and in the clinical study report.

Any other BLQ concentrations will be assigned a value of zero if they precede quantifiable samples in the initial portion of the profile. A BLQ value that occurs between quantifiable data points, especially prior to C_{max} , will be evaluated to determine if an assigned concentration of zero makes sense, or if reanalysis or exclusion of the data is warranted. Following C_{max} , BLQ values embedded between 2 quantifiable data points will be treated as missing. If BLQ values occur at the end of the collection interval (after the last quantifiable concentration), these will be set to missing data. If consecutive BLQ concentrations are followed by quantifiable concentrations in the terminal portion of the concentration curve, these quantified values will be excluded from the PK analysis by assigning them a value of missing, unless otherwise warranted by the concentration-time profile.

No imputations will be made for any dropouts and missing data.

4.2.2 Secondary Endpoint

4.2.2.1 Definition

4.2.2.1.1 Adverse events

Adverse Events

The term AE is used to include both serious and nonserious AEs and can include a deterioration of a pre-existing medical occurrence. AEs will be collected from the time of signature of informed consent through Day 151.

Treatment-Emergent Adverse Events

A treatment-emergent adverse event (TEAE) will be defined as an AE with the start date on or after the administration date, and up to Day 151.

Serious Adverse Events

AEs and SAEs will be collected from the time of signature of informed consent through Day 151.

Treatment-Emergent Serious Adverse Events

A treatment-emergent serious adverse event (TESAE) will be defined as a SAE with the start date and time on or after the administration date and time, and up to Day 151.

Adverse Events of Special Interest

The occurrence of AESIs defined as AEs of anaphylaxis and other serious hypersensitivity reactions, including immune complex disease (eg, vasculitis, endocarditis, neuritis, glomerulonephritis), or thrombocytopenia following investigational product administration. The SMQ broad and narrow for anaphylaxis, SMQ narrow for hypersensitivity and PT for thrombocytopenia and immune complex disease will be used to extract AESI terms.

New Onset Chronic Disease

An NOCD is a newly diagnosed medical condition that is of a chronic, ongoing nature. It is observed after receiving the investigational product and is assessed by the Investigator as medically significant. Examples of NOCDs include, but are not limited to diabetes, autoimmune disease (eg, lupus, rheumatoid arthritis), and neurological disease (eg, epilepsy). Events that would not be considered as NOCDs are mild eczema, diagnosis of a congenital anomaly present at study entry, or acute illness (eg, upper respiratory infection, otitis media, bronchitis).

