4.2.2.4 Primary Analysis of Secondary Endpoint

Safety endpoints include:

- Occurrence of all treatment-emergent adverse events (TEAEs), treatment-emergent serious adverse events (TESAEs), adverse events of special interest (AESIs), and new onset chronic diseases (NOCDs).
- Clinical laboratory assessments, vital signs.

ADA endpoints will be summarized as incidence of ADA to nirsevimab in serum.

The primary analysis of secondary endpoints will be summarized by number and percentage for qualitative variables, using the as-treated population. Quantitative variables will be summarized by subjects (n), mean, SD, median, minimum and maximum. Those variables details are described below:

Adverse Events

All AEs will be coded using MedDRA version 23.1 or higher by system organ class and preferred term. Specific AEs will be counted once for each subject for calculating rates but will be presented in total in subject listings. In addition, if the same AE occurs multiple times within a particular subject, the highest severity and level of causality will be reported. AEs will be captured on CRF page “Adverse Event”.

All AEs, both in terms of current MedDRA preferred term and CTCAE grade, will be summarized descriptively by count (n) and percentage (%) for each treatment group. The current MedDRA dictionary will be used for coding. The majority of the AE summaries, unless stated otherwise, will be based on TEAEs. Any AE occurring before study treatment (i.e. before the administration of the first dose on Study Day 1) will be included in the AE listings, but will not be included in the summary tables (unless otherwise stated). These will be referred to as ‘pre-treatment’. However, any AE occurring before the administration of the first dose on Study Day 1 that increases in severity after the first dose will be regarded as treatment emergent and thus will be included in the majority of summary tables.

Treatment-Emergent Adverse Events

All TEAEs will be summarized overall and by MedDRA system organ class and preferred term, severity, and relationship to investigational product.

Severity is classed according to NCI Common Terminology Criteria for Adverse Events (CTCAE) Version 5.0, grade 1-5. Severity will be presented as Grade 1 to 5 (increasing severity), which corresponds to the 5 classes. TEAEs of each severity grade will be summarized by SOC/PT.

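### The SAP's definition section and analysis section classify pre-injection dosing-day events and worsening pre-dose events in opposite ways, and TESAEs are timed differently from TEAEs

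*SAP*

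**What the plan says.** Section 4.2.2.1.1 holds the definitions. A TEAE "will be defined as an AE with the start date on or after the administration date, and up to Day 151". A TESAE is "a SAE with the start date and time on or after the administration date and time, and up to Day 151". Neither definition mentions an event that began before dosing and worsened afterwards.

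Section 4.2.2.4 says how events enter the tables. An event before the dose on Study Day 1 goes to the listings, "but will not be included in the summary tables (unless otherwise stated"), and is labelled pre-treatment. The same paragraph makes an exception for a pre-dose event "that increases in severity after the first dose will be regarded as treatment emergent", which then enters most tables. Later in that section, a TESAE is identified by the seriousness answer on the CRF, with no timing rule of its own.

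Section 4.2.2.2, where a derivation could have settled this, is marked as not applicable. The Appendix counts an event with a completely missing onset date as a TEAE. It gives rules for partial dates but none for a missing onset time.

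**The concern.** Occurrence of TEAEs and TESAEs is a named safety endpoint (SAP Table 5), and section 4.2.2.4 bases most adverse event summaries on TEAEs. If the two sections disagree on what is treatment emergent, two programmers who each follow the SAP faithfully can report different counts from the same data.

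The events in question can occur. Adverse events are collected from informed consent, so pre-dose events enter the database. Day 1 has pre-dose PK and ADA sampling (Tables 1 and 3), so an event on the dosing day before the injection is plausible.

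A TESAE would also normally be a TEAE that is serious. With different timing rules for the two terms, that no longer holds, and the TEAE and TESAE tables need not reconcile.

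**Working it through.** The SAP gives no figure to reproduce here. The check applies each stated rule to each type of event, taking a worsening as part of the same record.

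| Event | TEAE by 4.2.2.1.1 (date only) | TESAE by 4.2.2.1.1 (date and time) | Treatment emergent by 4.2.2.4 |
|---|---|---|---|
| Nonserious, Day 1 before injection, no worsening | Yes | n/a | No |
| Serious, Day 1 before injection, no worsening | Yes | No | No |
| Nonserious, before Day 1, worsens after dosing | No | n/a | Yes |
| Serious, before Day 1, worsens after dosing | No | No | Yes |
| Serious, Day 1 before injection, worsens after dosing | Yes | No | Yes |
| Onset after injection, up to Day 151 | Yes | Yes if serious | Yes |

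The rules agree throughout only in the last row. In rows 1 and 2 the definition section admits an event that the analysis section removes. In rows 3 and 4 the reverse happens. In rows 2 and 5 a serious event is a TEAE by definition but not a TESAE.

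Partial onset dates do not add to the dosing-day conflict. Where the known year, or year and month, match those of dosing, the Appendix imputes the onset to at least one day after dosing. The dosing-day conflict therefore concerns fully dated onsets only.

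Scale, from the planned arm sizes in section 1.3 (about 18 nirsevimab, about 6 placebo):
- One subject reclassified on nirsevimab: 1/18 = 0.0556, or 5.6 percentage points.
- One subject reclassified on placebo: 1/6 = 0.1667, or 16.7 percentage points.

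These are the steps in which any rate moves in arms of this size. They do not estimate how many events will be affected.

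**The case against.** The strongest reply is that little will change in practice. The date conflict covers only the hours before one injection, and the worsening conflict needs a healthy adult with a pre-dose event that later becomes more severe. The affected number may be zero. All analyses are descriptive, every adverse event is listed, and section 4.2.2.4 plans an SAE summary that is not expressly limited to treatment-emergent events. That limits the severity but does not remove the contradiction.

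A second reply is that section 4.2.2.1.1 allows a deterioration of a pre-existing condition to be an adverse event. If a worsening is entered as a new event with its own start date, it meets both definitions and the worsening conflict disappears. That is correct as far as it goes. The recording convention may sit in the protocol or CRF guidance, which are not shown; the SAP does not state it, and section 4.2.2.4 speaks of the same event increasing in severity. For this reason one cannot conclude that a worsening pre-dose event can never become a TESAE.

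A third reply is that section 4.2.2.4 only elaborates the definitions. It does not, because it removes events that the date rule includes and adds events that the date rule excludes.

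A reader might also infer that the Day 151 limit discards events reported at a late final visit, because Table 1 allows 10 days either side of 150 days. The SAP does not support this. Table 1 assigns PK samples only, adverse event collection is itself stated to run through Day 151, and sections 3.1 and 4.2.2.4 also use Day 151 as the name of the last visit.

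**Conclusion.** The inconsistency is real and can be seen from the current text alone. Sections 4.2.2.1.1 and 4.2.2.4 give opposite classifications for a dosing-day event that began before the injection, and for an event that began before the dosing day and worsened after dosing. The second holds on the assumption that the worsening is not recorded as a new event. Separately, a serious pre-injection event on Day 1 is a TEAE but not a TESAE.

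This should be fixed but is not critical. Safety is a secondary objective, so the tables affected are the main TEAE and TESAE summaries and not the primary PK analysis. The number of affected events cannot be derived from the SAP. It would also go too far to say that pre-injection events are attributed to nirsevimab: the IP-related tables use the investigator's causality assessment, and the date rule applies to both arms alike.

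**What to change.** Use one definition, worded identically in sections 4.2.2.1.1 and 4.2.2.4:

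- A TEAE is an adverse event with onset at or after dosing, compared by date and time where time is recorded, or a pre-dose event that increases in severity after dosing, up to Day 151 as already stated.
- A dosing-day onset with unknown time counts as a TEAE. A completely missing onset also counts, as the Appendix already provides.
- A TESAE is a serious TEAE. Delete its separate timing rule.

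The cost is a wording change in the SAP and matching programming specifications. The limit is that the SAP does not show that onset time is captured for every event: the listing in section 4.2.2.4 names the start date and study day but no time, and the Appendix handles dates only. Where time is not captured, dosing-day events would still be classified by date. The plan should say so, so that the rule is at least the same in every table.
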